4.3. Life Style Guidelines

4.3.1. Contraception

Female participants of childbearing potential and at risk for pregnancy must agree to use a highly effective method of contraception from the time of the first negative pregnancy test at Screening, throughout the study and for at least 17 days after the last dose of dacomitinib.

All female participants who, in the opinion of the investigator, are biologically capable of having children and are sexually active must agree to use a highly effective method of contraception consistently and correctly for the duration of the active treatment period and for at least 17 days after the last dose of investigational product. The investigator or his/her designee, in consultation with the participant, will select the most appropriate method of

contraception for the individual participant from the permitted list of contraception methods (see below) and instruct the participant in its consistent and correct use. Participants need to affirm that they meet at least one of the selected methods of contraception. The investigator or his/her designee, at each study visit, will discuss with the participant the need to use highly effective contraception consistently and correctly and document such conversation in the participant's chart. In addition, the investigator or his/her designee will instruct the participant to call immediately if the selected contraception method is discontinued or if pregnancy is known or suspected. Male participants should use a condom, if their partners are pregnant or if they plan to father a child.

Highly effective methods of contraception are those that, alone or in combination, result in a failure rate of less than 1% per year when used consistently and correctly (ie, perfect use) and include the following:

1. Established use of oral, inserted, injected, or implanted hormonal methods of contraception is allowed provided the participant plans to remain on the same treatment throughout the entire study and has been using that hormonal contraceptive for an adequate period of time to ensure effectiveness.
2. Correctly placed copper-containing IUD.
3. Male condom or female condom used WITH a spermicide (ie, foam, gel, film, cream, or suppository). For countries where spermicide is not available or condom plus spermicide is not accepted as highly effective contraception, this option is not appropriate.
4. Male sterilization with absence of sperm in the postvasectomy ejaculate.
5. Bilateral tubal ligation / bilateral salpingectomy or bilateral tubal occlusive procedure (provided that occlusion has been confirmed in accordance with the device's label).

4.3.2. Sunlight Exposure

Participants should avoid extended unprotected exposure to sunlight (eg, sunbathing) or tanning for the duration of the study period and for approximately 4 weeks after last dose of study drug. At the time of initiation of dacomitinib, use of moisturizers and appropriate measures to limit sun exposure should be initiated.

5. STUDY INTERVENTION

Study intervention is defined as any investigational intervention(s), marketed product(s), placebo, or medical device(s) intended to be administered to a study participant according to the study protocol.

ARM name	Dacomitinib 45 mg
Intervention name	Dacomitinib
Type	Small molecule
Dosage form	Tablet
Dose strength	15 mg
Dosage	Starting dose of 45 mg once a day
Route of administration	Oral
Sourcing	Provided centrally by the Sponsor
Packaging and labeling	Study intervention will be provided in bottles. Each bottle will be labeled as required per country requirement
Current/former name(s) or alias(es)	PF-00299804/dacomitinib

5.1. Allocation to Intervention/Treatment

This is an open-label study; however, the specific intervention to be taken by a participant will be assigned using an IVRS/IWRS. The site will contact the IVRS/IWRS prior to the start of study intervention administration for each participant. The site will record the intervention assignment on the applicable CRF, if required.

The investigator's knowledge of the treatment should not influence the decision to enroll a particular participant or affect the order in which participants are enrolled.

5.2. Drug Supplies

5.2.1. Dosage Form(s) and Packaging

Dacomitinib will be supplied by Pfizer Global Clinical Supply for oral administration as 15 mg tablets in HDPE bottles with desiccant and labeled according to local regulatory requirements.

Packaging and labeling for all study drugs will be in accordance with applicable local regulatory requirements and applicable Good Manufacturing Practice guidelines. The information on the study drug will be in accordance with approved submission documents.

Drug supplies will be shipped to the study sites with a Drug Shipment and Proof of Receipt form. This form will be completed and filed, as directed on the bottom of the Drug Shipment and Proof of Receipt form. The investigator must take responsibility for and must take all steps to maintain appropriate records and ensure appropriate supply, storage, handling, distribution, and usage of investigational product in accordance with the protocol and any applicable laws and regulations.

Refer to the Investigational Product Manual for further details.

5.3. Administration

The product will be administered in accordance with the India LPD.

The recommended dosage of dacomitinib is 45 mg taken orally once a day at approximately the same time each day, until disease progression, participant refusal/lost to follow-up, or unacceptable toxicity occurs. Dacomitinib can be taken with or without food.

The participant should take dacomitinib the same time each day. If the participant vomits or misses a dose, he/she should not take an additional dose or make up a missed dose but continue with the next scheduled dose.

The dose of dacomitinib should be reduced for adverse reactions as described in Table 1. Dose modifications for specific adverse reactions are provided in Table 2.

Table 1. Dacomitinib Recommended Dose Reductions for Adverse Reactions

Dose level	Dose (Once a Day)
First dose reduction	30 mg
Second dose reduction	15 mg

Table 2. Dacomitinib Dose Modifications for Adverse Reactions

Adverse Reaction	Severity ^a	Dosage Modification
Interstitial lung disease	Any Grade	
Permanently discontinue dacomitinib.
Diarrhea	Grade 2	
Withhold dacomitinib until recovery to less than or equal to Grade 1; then resume dacomitinib at the same dose level.For recurrent Grade 2 diarrhea, withhold until recovery to less than or equal to Grade 1; then resume dacomitinib at a reduced dose.
	Grade 3 or 4	
Withhold dacomitinib until recovery to less than or equal to Grade 1; then resume dacomitinib at a reduced dose.
Dermatologic Adverse Reactions	Grade 2	
Withhold dacomitinib for persistent dermatologic adverse reactions; upon recovery to less than or equal to Grade 1, resume dacomitinib at the same dose level.For recurrent persistent Grade 2 dermatologic adverse reactions, withhold until recovery to less than or equal to Grade 1; then resume dacomitinib at a reduced dose.
	Grade 3 or 4	
Withhold dacomitinib until recovery to less than or equal to Grade 1; then resume dacomitinib at a reduced dose.
Other	Grade 3 or 4	
Withhold dacomitinib until recovery to less than or equal to Grade 2; then resume dacomitinib at a reduced dose.

^a NCI CTCAE Version 4.03.

If a participant cannot tolerate treatment after a dose reduction to 15 mg, treatment will be permanently discontinued.

If a participant fails to recover within 2 weeks of interruption for a drug-related AE, treatment will be discontinued unless there is discussion of the clinical circumstance with the Sponsor and agreement that the participant may resume treatment after an interruption of greater than 2 weeks.

If a participant subsequently tolerates treatment well at the reduced level in the judgment of the investigator, the dose may be increased to the next dose level.

5.4. Drug Storage

The investigator, or an approved representative, eg, pharmacist, will ensure that all investigational products, including any comparative agents and/or marketed products are stored in a secured area with controlled access under recommended storage conditions and in accordance with applicable regulatory requirements.

Investigational product should be stored in its original container and in accordance with the India LPD. See the Investigational Product Manual for storage conditions of the product.

Storage conditions stated in the SRSD will be superseded by the storage conditions stated in the labeling.

Site systems must be capable of measuring and documenting (for example, via a log), at a minimum, daily minimum and maximum temperatures for all site storage locations (as applicable, including frozen, refrigerated and/or room temperature products). This should be captured from the time of investigational product receipt throughout study, on all business days. Even for continuous monitoring systems, a log or site procedure which ensures active daily evaluation for excursions should be available. The operation of the temperature monitoring device and storage unit (for example, refrigerator), as applicable, should be regularly inspected to ensure it is maintained in working order.

Any excursions from the India LPD storage conditions should be reported upon discovery. The site should actively pursue options for returning the product to labeled storage conditions, as soon as possible. Deviations from the storage requirements, including any actions taken, must be documented and reported to the Sponsor.

Once an excursion is identified, the investigational product must be quarantined and not used until the Sponsor provides documentation of permission to use the investigational product. Specific details regarding information the site should report for each excursion will be provided to the site.

Receipt of materials, door opening and closing, and other routine handling operations where the product(s) are briefly out of labeled temperature range are not considered excursions.

Site staff will instruct participants on the storage requirements for take home medications including how to report temperature excursions.

The Investigational Product Manual should be referenced for any additional guidance on storage conditions and actions to be taken when conditions are outside the specified range.

5.5. Drug Accountability

The investigator, institution, or the head of the medical institution (where applicable) is responsible for study intervention accountability, reconciliation, and record maintenance (ie, receipt, reconciliation, and final disposition records). All study interventions will be accounted for using an investigational product accountability form/record. Further guidance and information for the final disposition of unused study interventions are provided in the Investigational Product Manual.

Participants will be required to return all unused dacomitinib tablets at every cycle. The number of tablets returned by the participant should be counted, documented, and recorded by site personnel to support the accountability process. Study site personnel must make reasonable efforts to obtain study drug packaging and any unused tablets from participants who do not routinely return them at study site visits. Unreturned tablets will be considered to have been taken unless reported otherwise by the participant. For additional information regarding accountability, please refer to the Investigational Product Manual.

The Sponsor or designee will provide guidance on the destruction of unused study intervention (eg, at the site). If destruction is authorized to take place at the investigator site, the investigator must ensure that the materials are destroyed in compliance with applicable environmental regulations, institutional policy, and any special instructions provided by Pfizer, and all destruction must be adequately documented.

5.6. Concomitant Treatment(s)

The use of permitted concomitant medication must be in accordance with the India LPD.

All concomitant medications and non-drug supportive interventions should be recorded in the CRF from 28 days prior to start of study treatment and up to 28 days after the last dose of study treatment.

Any medication or vaccine (including over-the-counter or prescription medicines, vitamins, or herbal supplements) that the participant is receiving at the time of enrollment or receives during the study must be recorded along with reason for use and dates of administration including start and end dates.

The medical monitor should be contacted if there are any questions regarding concomitant or prior therapy.

5.6.1. Prohibited Concomitant Treatments

Concomitant use with a PPI decreases dacomitinib concentrations, which may reduce dacomitinib efficacy. The concomitant use of PPIs with dacomitinib should be avoided. As an alternative to PPIs, use locally-acting antacids or an H₂-receptor antagonist. Dacomitinib should be administered at least 6 hours before or 10 hours after taking an H₂-receptor antagonist.

Concomitant use of dacomitinib increases the concentration of drugs that are CYP2D6 substrates which may increase the risk of toxicities of these drugs. The concomitant use of dacomitinib with CYP2D6 substrates should be avoided as minimal increases in concentration of the CYP2D6 substrate may lead to serious or life-threatening toxicities.

Other Antitumor or Experimental Drugs

No additional systemic antitumor therapy will be permitted while participants are receiving a study therapy.

6. STUDY PROCEDURES

6.1. Screening

All participants being considered for the study and eligible for Screening must sign an informed consent for the study before completing any study-specific procedures. Participants will be screened within 28 days prior to first dosing of dacomitinib to confirm that they meet the eligibility criteria for the study. The required Screening assessments are summarized in the [Schedule of Activities](#) and [Section 7 Assessments](#).

6.2. Study Period

For study treatment period procedures, see [Schedule of Activities](#) and [Section 7 Assessments](#).

6.3. Follow-up Visit

All participants will return to the study site up to 28 days after the last dose of study drug administration for assessment of potential AEs, recording of concomitant treatment use and to confirm appropriate contraception usage.

6.4. Participant Withdrawal

Withdrawal of Consent: Participants who request to discontinue study treatment will remain in the study and must continue to be followed for protocol-specified follow-up procedures. The only exception to this is when a participant specifically withdraws consent for any further contact with him/her or persons previously authorized by participant to provide this information. Participants should notify the investigator of the decision to withdraw consent from future follow-up in writing, whenever possible. The withdrawal of consent should be explained in detail in the medical records by the investigator, as to whether the withdrawal is from further treatment with study drug only or also from study procedures and/or post treatment study follow-up, and entered on the appropriate CRF page.

Lost to Follow-Up: All reasonable efforts must be made to locate participants to determine and report their ongoing status. This includes follow-up with persons authorized by the participant as noted above. Lost to follow-up is defined by the inability to reach the participant after a minimum of 3 documented phone calls, faxes, or emails as well as lack of response by participant to 1 registered mail letter. All attempts should be documented in the participant's medical records. If it is determined that the participant has died, the site will use permissible local methods to obtain the date and cause of death. If investigator's use of third-party representative to assist in the follow-up portion of the study has been included in the participant's informed consent, then the investigator may use a Sponsor retained third-party representative to assist site staff with obtaining participant's contact information or other public vital status data necessary to complete the follow-up portion of the study. The site staff and representative will consult publicly available sources, such as public health registries and databases, in order to obtain updated contact information. If after all attempts, the participant remains lost to follow-up, then the last known alive date as determined by the investigator should be reported and documented in the participant's medical records.

Participants may withdraw from the study at any time at their own request, or they may be withdrawn at any time at the discretion of the investigator.

If a participant does not return for a scheduled visit, every effort should be made to contact the participant. All attempts to contact the participant and information received during contact attempts must be documented in the participant's medical record. In any circumstance, every effort should be made to document participant outcome, if possible. The investigator should inquire about the reason for withdrawal, request the participant to return for a final visit, if applicable, and follow up with the participant regarding any unresolved AEs.

If the participant withdraws from the study, and also withdraws consent for disclosure of future information, no further evaluations should be performed, and no additional data should be collected. The Sponsor may retain and continue to use any data collected before such withdrawal of consent.

7. ASSESSMENTS

7.1. Antitumor Activity Assessments

7.1.1. Tumor Assessments

Tumor assessments will include all known or suspected disease sites. CT or MRI scans of CAP and MRI of the brain will be performed at Screening and repeated every 12 weeks \pm 1 week until the end of treatment. For all tumor assessments, the method of assessment that was used at Screening should be the same method used throughout the study. Tumor assessment should be repeated at the end of treatment if more than 6 weeks have passed since the last evaluation.

Assessment of response will be made using RECIST version 1.1 ([Appendix 1](#)).⁹
Confirmation of response will be required \geq 4 weeks after initial response is observed.

7.2. Safety Assessments

The following parameters will be assessed at time points detailed in [Schedule of Activities](#). Unscheduled clinical laboratory measurements may be obtained at any time during the study to assess any perceived safety concerns.

- Physical examinations and vital signs;
- ECOG PS;
- Safety laboratory data;
- 12-lead ECG.

7.2.1. Physical Examinations and Vital Signs

Participants will have a physical examination to include major body systems, body weight, blood pressure and pulse rate at the time points described in the [Schedule of Activities](#). Blood pressure and pulse rate should be taken pre-dose with the participant in the seated position after the participant has been sitting quietly for at least 5 minutes. Investigators should pay special attention to clinical signs related to previous serious illnesses.

7.2.2. Electrocardiograms

ECG will be obtained as outlined in the [Schedule of Activities](#) using an ECG machine that automatically calculates the heart rate and measures PR interval, QRS complex, QT interval, and QTcF.

Three (3) consecutive 12-lead ECGs pre-dose will be performed approximately 2 minutes apart to determine mean PR interval, QRS complex, and QTcF at baseline (Screening and Cycle 1 Day 1, if the ECG at Screening was performed more than 7 days before Cycle 1 Day 1). Additional ECGs may be collected as clinically indicated and as single ECGs.

If the participant experiences signs or symptoms of a cardiac or neurologic disorder (specifically syncope, dizziness, seizures, or stroke), ECG should be obtained at the time of the event.

If there is finding of QTcF >500 msec, the ECG must be repeated. If there is finding of QTcF >500 msec again (ie, \geq CTCAE Grade 3), the ECG must be reviewed by qualified personnel at the site as soon as the finding is made, including verifying that the machine reading is accurate and that the Fridericia's correction formula is applied.

An electronic reading of prolonged QTc must be confirmed by a manual reading. Before concluding that an episode of QTc prolongation is due to study drug, thorough consideration should be given to potential precipitating factors (eg, a change in the participant's clinical condition, the effect of concurrent medication, electrolyte disturbance) and a possible evaluation by a specialist. If the QTcF reverts to \leq 500 msec, and it is the opinion of the

investigator and the Sponsor that the prolongation was not due to the study drug, treatment may be continued with regular ECG monitoring.

7.2.3. ECOG PS

Refer to [Appendix 2](#) for ECOG PS criteria.

7.2.4. Clinical Safety Laboratory Assessments

The required laboratory tests are listed in [Appendix 3](#). Hematology and blood chemistry will be collected at the time points described in the [Schedule of Activities](#) table and analyzed at local laboratories. Laboratory tests may also be performed when clinically indicated. Local laboratory certification(s) and reference ranges should be provided to the Sponsor prior to study participant screening activity.

7.2.5. Pregnancy Testing

For female participants of childbearing potential, a serum or urine pregnancy test, with sensitivity of at least 25 mIU/mL, will be performed before investigational product administration at the screening visit, on Day 1 of every cycle and at the end of treatment visit. A negative pregnancy result is required before the participant may receive the investigational product. Pregnancy tests will also be done whenever one menstrual cycle is missed during the active treatment period (or when potential pregnancy is otherwise suspected) to confirm the participant has not become pregnant during the study. In the case of a confirmed pregnancy, the participant will be withdrawn from study medication and from the study. Pregnancy tests may also be repeated as per request of IRB/IECs or if required by local regulations.

8. ADVERSE EVENT REPORTING

8.1. Adverse Events

All observed or volunteered AEs regardless of treatment group or suspected causal relationship to the investigational product(s) will be reported as described in the following sections.

For all AEs, the investigator must pursue and obtain information adequate both to determine the outcome of the AE and to assess whether it meets the criteria for classification as an SAE requiring immediate notification to Pfizer or its designated representative. For all AEs, sufficient information should be obtained by the investigator to determine the causality of the AE. The investigator is required to assess causality. Follow-up by the investigator may be required until the event or its sequelae resolve or stabilize at a level acceptable to the investigator, and Pfizer concurs with that assessment.

As part of ongoing safety reviews conducted by the Sponsor, any nonserious AE that is determined by the Sponsor to be serious will be reported by the Sponsor as an SAE. To assist in the determination of case seriousness, further information may be requested from the investigator to provide clarity and understanding of the event in the context of the clinical study.

8.2. Reporting Period

For SAEs, the active reporting period to Pfizer or its designated representative begins from the time that the participant provides informed consent, which is obtained prior to the participant's participation in the study, ie, prior to undergoing any study-related procedure and/or receiving investigational product, through and including 28 calendar days after the last administration of the investigational product. SAEs occurring to a participant after the active reporting period has ended should be reported to the Sponsor if the investigator becomes aware of them; at a minimum, all SAEs that the investigator believes have at least a reasonable possibility of being related to study drug are to be reported to the Sponsor.

AEs (serious and nonserious) should be recorded on the CRF from the time the participant has taken at least 1 dose of study treatment through the last participant visit.

If a participant begins a new anticancer therapy, the AE recording period for nonserious AEs ends at the time the new treatment is started. SAEs and deaths must be recorded and reported if they occur during the SAE reporting period after the last dose of investigational product, irrespective of any intervening treatment. Note that a switch to a commercially available version of the study intervention is considered as a new anticancer therapy for the purposes of SAE reporting.

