7. Tumor assessment should be repeated at the end of treatment if more than 6 weeks have passed since the last evaluation.
8. AE assessments: AEs should be documented and recorded into the eCRF at each visit using NCI CTCAE version 4.03.

For SAEs, the active reporting period to Pfizer or its designated representative begins from the time that the participant provides informed consent, which is obtained prior to the participant's participation in the study, ie, prior to undergoing any study-related procedure and/or receiving investigational product, through and including 28 calendar days after the last administration of the investigational product. SAEs occurring to a participant after the active reporting period has ended should be reported to the Sponsor if the investigator becomes aware of them; at a minimum, all SAEs that the investigator believes have at least a reasonable possibility of being related to study drug are to be reported to the Sponsor. AEs (serious and nonserious) should be recorded on the CRF from the time the participant has taken at least 1 dose of study treatment through the last participant visit. If a participant begins a new anticancer therapy, the AE recording period for nonserious AEs ends at the time the new treatment is started. SAEs and deaths must be recorded and reported if they occur during the SAE reporting period after the last dose of investigational product, irrespective of any intervening treatment. Note that a switch to a commercially available version of the study intervention is considered as a new anticancer therapy for the purposes of SAE reporting.

9. Concomitant medications and non-drug supportive interventions: all concomitant medications and non-drug supportive interventions should be recorded in the CRF from 28 days prior to start of study treatment and up to 28 days after the last dose of study treatment.

TABLE OF CONTENTS

LIST OF TABLES	12
APPENDICES	13
1. INTRODUCTION	14
1.1. Mechanism of Action/Indication.....	14
1.2. Background and Rationale	14
1.2.1. Background.....	14
1.2.2. Rationale	15
2. STUDY OBJECTIVES AND ENDPOINTS.....	15
3. STUDY DESIGN.....	16
4. PARTICIPANT SELECTION.....	16
4.1. Inclusion Criteria.....	16
4.2. Exclusion Criteria.....	17
4.3. Life Style Guidelines.....	18
4.3.1. Contraception.....	18
4.3.2. Sunlight Exposure.....	19
5. STUDY INTERVENTION.....	19
5.1. Allocation to Intervention/Treatment.....	20
5.2. Drug Supplies	20
5.2.1. Dosage Form(s) and Packaging.....	20

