3. ENDPOINTS AND BASELINE VARIABLES: DEFINITIONS AND CONVENTIONS

3.1. Primary Endpoint

The primary endpoint is the incidence of AEs, defined as the number of participants with treatment-emergent adverse events (TEAEs) from the time of first dose to 28 days post last dosing date or the date prior to initiation of a new anticancer therapy, divided by the number of participants in the Safety Set (see [Section 4](#)).

An adverse event is considered treatment-emergent if any of the following apply:

- The event occurs on-treatment (defined in [Section 3.5](#)) and was not seen prior to the start of treatment.
- The event was seen prior to the start of treatment but increased in National Cancer Institute Common Terminology Criteria for Adverse Events (NCI CTCAE) v4.03 grade while on-treatment.

Treatment-emergent adverse events will be characterized by type, frequency, severity (as graded by the investigator according to NCI CTCAE version 4.03 and coded by the Sponsor using Medical Dictionary for Regulatory Activities [MedDRA]), timing, seriousness, and relationship to dacomitinib.

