5.3.2. Handling of Incomplete or Missing Dates

5.3.2.1. Adverse Events

AE Onset Date:

The following imputation rules apply if the event is unique for a participant or it is the first of a series of similar events; otherwise, the AE Onset Date will not be imputed:

- If the AE Collection Date is not missing, is less than the Date of First Exposure to Treatment, and is less than the AE Stop Date, then AE Onset Date is set to the Date of AE Collection.
- If the Previous Visit Date is greater than the Date of First Exposure to Treatment and less than the AE Stop Date, the AE Onset Date is set to the previous visit date.
- If the Date of First Exposure to Treatment is greater than the previous visit date and less than the AE Stop Date, the AE Onset Date is set to the Date of First Exposure to Treatment.
- Otherwise AE Onset date is set to the AE Stop date.

AE Stop Date:

Ongoing events will have the AE Stop Date set to one of the following values:

- Date of Death, if the participant died and a date of death exists.
- Maximum of (Withdraw date, AE Onset Date, AE Collection Date) if the participant withdrew from the study and a date of withdraw exists.

- Maximum of (AE Onset Date, Subject Summary Collection Date, AE Collection Date) if the Subject Summary CRF page exists but a date of withdraw does not exists.
- Maximum of (Last Treatment Date, AE Onset Date) if no Subject Summary page exists.

Imputation will only occur if event is unique for the participant, or it is the last of a series of similar events; otherwise the Stop Date will not be imputed. Adverse Events are deemed similar if they have the same verbatim term.

Resolved events will have the AE Stop Date set to the maximum of the AE collection date and the AE Onset date.

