5.3.3. Missing Toxicity Grade of Adverse Events

Prior to Study Treatment: If no toxicity grade is available or the grade is reported as unknown for an adverse event prior to the first study treatment, then Grade 1 will be assumed for purposes of defining a baseline grade.

In summaries which present maximum toxicity grade, the maximum of non-missing grades will be displayed. Missing grade will only be displayed for cases where a participant reported only one event and the grade is missing.

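### CRF recording of AEs starts at the first dose, but the treatment-emergent rule needs pre-dose events and their grades, so pre-existing symptoms cannot be reliably separated by grade

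*Protocol*

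**What the plan says.** Protocol 8.2, repeated in footnote 8 of the Schedule of Activities, sets the start of CRF collection: "AEs (serious and nonserious) should be recorded on the CRF from the time the participant has taken at least 1 dose of study treatment". Footnote 8 opens with a different instruction: "AEs should be documented and recorded into the eCRF at each visit using NCI CTCAE version 4.03". The AE row of the Schedule is marked in every column, Screening included.

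The SAP builds the primary endpoint on treatment-emergent AEs (SAP 3.1). The definition has two limbs:

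- an on-treatment event that "was not seen prior to the start of treatment";
- a pre-existing event that worsened: "The event was seen prior to the start of treatment but increased in National Cancer Institute Common Terminology Criteria for Adverse Events" (version 4.03) while on treatment.

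Other SAP sections provide for AE records made before dosing. If a pre-dose AE has no grade, "then Grade 1 will be assumed for purposes of defining a baseline grade" (SAP 5.3.3). The first onset-date imputation rule is for an AE whose collection date "is less than the Date of First Exposure to Treatment, and is less than the AE Stop Date" (SAP 5.3.2.1). SAP 6.1.1 flags AEs that are not treatment-emergent in the listings.

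Medical history is taken at Screening. SAP 6.5.1.2 codes it and summarises past and present conditions separately. It mentions no grade, and SAP 3.1 does not refer to medical history.

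**The concern.** The protocol gives sites two incompatible instructions on whether a pre-dose AE goes on the CRF. The more explicit one, in 8.2, excludes the data that the primary analysis uses as its comparator. Participants have metastatic lung cancer and ECOG performance status 0-2, and inclusion criterion 7 admits unresolved effects of earlier therapy that the investigator does not consider a safety risk. Cough, dyspnoea, fatigue or loss of appetite at entry is therefore plausible.

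At stake are the tables by preferred term and maximum grade in SAP 6.1.1, all-causality and treatment-related. The study has one arm, so no comparator group would show the same background error.

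**Working it through.** **1. The plan's own figure.** Protocol 9.2 gives a maximum standard error of 0.05 with 100 participants. √(0.5 × 0.5 / 100) = 0.05, so it reproduces. It does not depend on this point, which concerns collection and classification.

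**2. What each limb needs, and what 8.2 supplies.**

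| SAP element | Needs | Available if a site follows 8.2 |
|---|---|---|
| 3.1, first limb | Knowledge that the event was absent before dosing | No pre-dose AE record; medical history may show presence, but 3.1 does not link to it |
| 3.1, second limb | A pre-dose CTCAE grade | None on the AE page |
| 5.3.3, Grade 1 default | A pre-dose AE record without a grade | No such record. Where another site does make one, an unchanged Grade 2 symptom would count as worsened |
| 5.3.2.1, first onset rule | AE collected before first exposure | Cannot apply |

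**3. Missing onset date.** Take a symptom present before dosing and still ongoing afterwards, first entered after dose 1 with no onset date. With the first rule of SAP 5.3.2.1 unavailable, the others set onset to:

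- a previous visit later than first exposure; or
- the date of first exposure; or
- the stop date, which for an ongoing event is not before first exposure.

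Every remaining route gives an onset on or after first exposure. SAP 3.5 counts AEs on the day of first dose as on-treatment. Unless another source intervenes, the symptom will ordinarily be classed as treatment-emergent.

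**4. Illustrative size for one preferred term.** Let *t* be the true treatment-emergent rate, *b* the share of participants with a stable symptom at entry, and *m* the share of those misclassified. All three are assumptions; the documents give none of them.

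Reported rate = *t* + (1 − *t*) × *b* × *m*. With *t* = 10%:

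| *b* | *m* = 0.25 | *m* = 0.5 | *m* = 1 |
|---|---|---|---|
| 10% | 12.3% | 14.5% | 19.0% |
| 20% | 14.5% | 19.0% | 28.0% |
| 30% | 16.8% | 23.5% | 37.0% |

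For *b* = 10-30% the inflation runs from 0.9 × 0.10 × 0.25 = 2.25 points to 0.9 × 0.30 × 1 = 27 points.

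**5. The any-AE rate.** SAP 2.1.1 defines the primary variable as a yes/no indicator of any AE. With an assumed true rate of 95% and *m* = 1, *b* = 10% gives 0.95 + 0.05 × 0.10 = 95.5%, and *b* = 40% gives 0.95 + 0.05 × 0.40 = 97.0%. The shift is at most 2 points.

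**The case against.** The case for leaving the plan alone has real content.

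- **Presence is captured elsewhere.** Medical history and physical examination are done at Screening, and a pre-dose onset date on a later AE record identifies the event as pre-existing. This stands for presence but does not supply a baseline grade. If medical history were used as the source without a grade, a listed symptom that later worsened would fail the first limb and have no comparator for the second.
- **Protocol 8.3 asks for worsening of malignancy symptoms.** A stable cancer symptom therefore need not be entered, and a true worsening with no earlier AE record still counts under the first limb. Both points stand and narrow the error to stable symptoms entered as new. Section 8.3 does not make the same provision for comorbidities or residual effects of earlier therapy.
- **The Screening mark may refer only to SAEs**, whose reporting period "begins from the time that the participant provides informed consent". This is a possible reading of the mark, but it does not explain the opening sentence of footnote 8, which is not limited to SAEs.
- **The SAP rules are conditional.** SAP 5.3.2.1 and 5.3.3 handle pre-dose records if they exist and do not require them. That is correct, but the second limb of SAP 3.1 has no content without them.
- **The CRF is not among the documents.** Its medical history page may collect a grade. That cannot be excluded, and the plan should say so if it does.
- **Laboratory summaries are not affected**, because results are graded programmatically against baseline. This stands.

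**Conclusion.** The inconsistency is real and affects the data behind the primary endpoint. Followed as written, 8.2 leaves the increase-in-grade limb without a comparator and disables the only imputation rule that can place an ongoing event with missing onset before dosing. Whether graded pre-dose records exist will depend on which instruction each site follows.

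The likely error is upward and confined to per-term and per-grade rows for symptom-type events. The range of about 2 to 27 points rests wholly on the assumed *t*, *b* and *m*. A near-ceiling any-AE rate would hardly change.

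Three stronger readings are tempting but not supported:

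- *That pre-existing symptoms cannot be separated at all.* Medical history and onset dates can show presence; what is lost is reliable separation by grade.
- *That pre-dose SAEs in the safety database and on the CRF are a mismatch needing repair.* Protocol 8.2 states the different start times openly, and 8.13.2 asks for consistency only where both forms collect the same data.
- *That the bias is a fixed multiple of the 0.05 standard error.* That figure applies at a rate of 50%, the bias inputs are assumed, and simply multiplying prevalence by misentry ignores participants who also have a true event of the same term.

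**What to change.** Reconcile Protocol 8.2, footnote 8 and the Schedule so that AEs, and signs and symptoms ongoing before dose 1, are recorded on the CRF from informed consent with onset date and CTCAE 4.03 grade. Either the AE page or a graded medical history page would serve, provided one is specified for all sites.

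In SAP 3.1, state that each on-treatment event is compared with the last pre-dose grade of the same preferred term from that source. Pre-dose events would be listed but not summarised. If they are recorded on the AE page, the first onset rule in SAP 5.3.2.1 can operate as well.

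The cost is a wording change in each document and a few more CRF lines per participant over a screening period of at most 28 days. There is no new visit, and the 100 treated participants and the 0.05 maximum standard error are unchanged. The change is best made before dosing starts, because baseline grades can afterwards be recovered only in retrospect.
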